6.14.7.4. Injection Site Reactions (ISR)

Injection site reactions (ISRs) are AEs localized to the immediate site of the administration of a drug. The evaluation of study drug related ISRs will be through the unsolicited reporting of ISR TEAEs and through the use of an Injection Site Reaction Follow-up Form completed by the investigator for each ISR reported.

Injection site reactions will be defined using the MedDRA High Level Term (HLT) of Injection Site Reaction, excluding certain PTs (for example, those PTs related to injections into a joint).

Analyses will include:

- TE ISRs by PT.
- The additional data collected on the ISR follow-up form will be summarized in 2 distinct ways: at the patient level and at the event level. A by-patient listing of these data will be provided.

6.14.7.5. Cerebro-Cardiovascular Events

The cerebro-cardiovascular events reported in the study will be adjudicated by an independent, external adjudication committee (AC). All confirmed events after adjudication will be used for the analysis of cerebro-cardiovascular events. Categories of events include: Cardiovascular, Cerebrovascular and Peripheral Vascular Events. As detailed in the compound level safety standards, the categories are further categorized into subcategories.

Analyses will include:

- TE cerebro cardiovascular confirmed events by category, subcategory, and PT.
- By-patient listing for all patients having a TEAE of cerebro-cardiovascular (confirmed event, no event, or insufficient documentation for event determination) at any time.

6.14.7.6. Malignancies

Malignancies will be defined using PTs from the Malignant tumors SMQ. Malignant tumor events will be summarized separately for the categories: Non-Melanoma skin cancer (NMSC) and Malignancies excluding NMSC.

Analyses will include:

- TE malignancy by category and PT.
- By-patient listing for all patients having a TEAE of malignancy at any time.

6.14.7.7. Suicidal Ideation/Behavior and Depression

During the study, suicidal ideation and behavior, and depression will be assessed prospectively by the investigator via signs and symptoms and through the use of the Columbia-Suicide Severity Rating Scale (C-SSRS) and the QIDS-SR16. Analyses will include:

- C-SSRS: Only a listing of the C-SSRS will be provided. Additional summaries may be provided if justified by the number of events (further described in the compound level safety standards).
- QIDS-SR16: Shift tables will be provided showing the number and percentage of patients within each baseline category (maximum value) versus each postbaseline category (maximum value) by treatment. Additionally, outcomes such as any increase in depression will be compared between treatments (further described in the compound level safety standards).

6.15. Subgroup Analyses

6.15.1. Efficacy Subgroup Analyses

Subgroup analyses will be conducted for the primary endpoints of Week 16 PASI 90 and sPGA (0,1) proportion in the ITT Population. Also, subgroup analysis for the Week 52 PASI 90 and sPGA (0,1) proportion in the ITT population will be performed. The subgroups to be analyzed are listed in [Table AMAJ.6.4](#) along with the demographic characteristics. Some additional subgroup analyses may be performed to meet regulatory requirements in specific countries. Additional subgroup analyses, which are not based on baseline/demographic characteristics in [Table AMAJ.6.4](#) are:

- concomitant topical steroid product use: yes, no.
- concomitant systemic corticosteroid use: yes, no
- treatment-emergent antimirikizumab antibody status: positive, negative

The analysis of additional subgroups will not require an amendment to the SAP. Missing outcome data will be imputed using NRI. Within each subgroup category the proportion of responders by treatment, treatment differences and 95% CIs will be displayed. Also, p-values using Fisher's exact test for treatment comparison will be provided. If the number of patients in any subgroup category is <10% of the total population, only summaries of the efficacy data will be provided (that is, no inferential testing). Forest plots will be generated to display the odds ratios and 95% CIs for the efficacy subgroup analyses.

A logistic regression model with treatment, subgroup, and the interaction of subgroup by treatment will be used. The subgroup-by-treatment interaction will be tested using the Firth correction (Firth 1993) at the significance level of 0.10.

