Induction and Maintenance Periods*	ITT; Induction and Maintenance PPS	placebo/250 miri; 300 secu; 250 miri Q4W/125 miri Q8W; 250 miri Q4W/250 miri Q8W; Total miri/miri (Note: Total miri represents the combined treatments of 250 miri Q4W/125 miri Q8W and 250 miri Q4W/250 miri Q8W.)	250 miri Q4W/125 miri Q8W vs 300 secu; 250 miri Q4W/250 miri Q8W vs 300 secu (For efficacy/healthoutcome measures, the comparisons will be only conducted from Week 20 to Week 52)
All Active Treatment Periods	All Active Treatments Safety	placebo/250 miri; 300 secu; 250 miri Q4W/125 miri Q8W; 250 miri Q4W/250 miri Q8W; all miri (Note: all miri represents the combined treatments of placebo/250 miri, 250 miri Q4W/125 miri Q8W and 250 miri Q4W/250 miri Q8W.)	250 miri Q4W/125 miri Q8W vs 300 secu; 250 miri Q4W/250 miri Q8W vs 300 secu

Treatment Groups and Comparisons for Each Study Period and Analysis Population

Study Period	Analysis Population	Treatment Groups	Inferential Comparisons
All Active Treatment + Follow-up Periods	All Active Treatment Safety	300 secu + FUP; all miri + FUP (Note: the header with “+ FUP” is used to emphasize that the observations from Follow-up Period are included.)	
All Periods	ITT	For study disposition only: placebo/250 miri; 300 secu; 250 miri Q4W/125 miri Q8W; 250 miri Q4W/250 miri Q8W; Total miri/miri	
	Induction Safety Population	For hepatic plot only: Ever on miri; Never on miri	

Abbreviations: FUP = follow-up; ITT = intent-to-treat; miri = mirikizumab; PPS = per protocol set; Q4W = every 4 weeks; Q8W = every 8 weeks; secu = secukinumab.

* For some analyses based on response status at certain weeks (Week 16 or 24), only maintenance period will be used, and the placebo/250 miri treatment group might not be displayed.

Note: for immunogenicity analysis, 300 secu treatment group will be excluded, thus the comparisons involving 300 secu will not be conducted; also the outputs for the “All Active Treatment Period” and “All Active Treatment + Follow-up Periods” will be combined.

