6.14.6. Immunogenicity

An individual sample is potentially examined multiple times in a hierarchical procedure to produce a sample antidrug antibodies (ADA) assay result and potentially a sample neutralizing antidrug antibodies (NAb) assay result. A patient has treatment-emergent antidrug antibodies (TE-ADA) when ADAs are induced or boosted by exposure to study drug; that is, when at least 1 postbaseline ADA sample has a 4-fold increase in titer compared to baseline (if ADAs were present at baseline) or has a titer 2-fold greater than the minimum required dilution of 1:10 (if no ADAs were present at baseline).

Compound level safety standards will be followed in the analyses of immunogenicity. Listings of immunogenicity assessments will be provided-along with the summary of specified TEAEs by TE-ADA status. The summary of TE-ADA and NAb status will be produced for the 2 safety populations, where the postbaseline period for reporting is the same as described for AEs in Section 6.14.2. The subgroup analysis of efficacy by TE-ADA status (positive, negative) is described in the Section 6.15. Additional assessments of the relationship between immunogenicity and efficacy will be performed as part of the integrated analysis including other Phase 3 mirikizumab psoriasis trials.

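### Section 6.15.1 tests mirikizumab against placebo within TE-ADA status at Week 16, where the positive category has few or no placebo patients

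*SAP*

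**What the plan says.** SAP Section 6.15.1 plans subgroup analyses of PASI 90 and sPGA (0,1) at Weeks 16 and 52. Besides the baseline characteristics in Table AMAJ.6.4 it names three other subgroups: concomitant topical steroid use, concomitant systemic corticosteroid use, and "treatment-emergent antimirikizumab antibody status: positive, negative". None of the three is exempted from the common plan:

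- "Within each subgroup category the proportion of responders by treatment, treatment differences and 95% CIs will be displayed";
- Fisher's exact p-values, and forest plots of odds ratios;
- "The subgroup-by-treatment interaction will be tested using the Firth correction", at a significance level of 0.10.

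The one safeguard is a size rule: "If the number of patients in any subgroup category is <10% of the total population, only summaries of the efficacy data will be provided".

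Section 6.14.6 says that a patient has TE-ADA "when ADAs are induced or boosted by exposure to study drug", and adds: "The subgroup analysis of efficacy by TE-ADA status (positive, negative) is described in the Section 6.15".

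For the combined Induction and Maintenance Periods, Table AMAJ.6.2 lists only "250 miri Q4W/125 miri Q8W vs 300 secu; 250 miri Q4W/250 miri Q8W vs 300 secu". The note to that table says: "for immunogenicity analysis, 300 secu treatment group will be excluded, thus the comparisons involving 300 secu will not be conducted".

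**The concern.** A subgroup comparison needs patients from both arms in each category. TE-ADA status cannot supply them at Week 16. It arises from exposure to mirikizumab, and a placebo patient can be positive only by meeting the titer rule without exposure. The positive category is then a sizeable mirikizumab group set against a handful of placebo patients, or none. The size rule would not stop the analysis, because it looks at the category total and not at each arm.

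The negative category is estimable, but it sets a mirikizumab subset selected after baseline against nearly all placebo patients, so its treatment difference is not a randomised comparison either.

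At stake is how the exploratory TE-ADA and efficacy endpoint in Table AMAJ.4.1 is read. A forest-plot row and an interaction p-value resting on two or three placebo patients would sit beside valid baseline subgroups and look equally informative.

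**Working it through.** **Inputs from SAP Section 5.2.** 1443 patients at 4:4:4:1 give 1443 × 8/13 = 888 mirikizumab and 1443 × 1/13 = 111 placebo, as the SAP states. Assumed Week 16 sPGA (0,1) response is 70% and 5%.

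**Assumptions.** No TE-ADA rate is given. I take 20% on mirikizumab (178 positive, 710 negative); a range of 5% to 30% would be 44 to 266 positive. I take k = 0 to 6 placebo positives.

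**Size rule.** With 178 + 2 positives, the category is 180/999 = 18.0% of the mirikizumab and placebo patients, or 180/1443 = 12.5% of everyone. Testing goes ahead on two placebo patients. With no placebo positives, the rule stops testing only below 0.1 × 999/888 = 11.3% TE-ADA, or 0.1 × 1443/888 = 16.3%, depending on which total is meant.

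**Interaction estimate, true ratio 1.** In a treatment-by-subgroup model the Firth penalty adds 0.5 to each cell. With k = 0 the interaction is not estimable. For k = 2, both nonresponders:

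- Positives: mirikizumab odds (124.6 + 0.5)/(53.4 + 0.5) = 2.32; placebo odds 0.5/2.5 = 0.20; odds ratio 11.6.
- Negatives: mirikizumab odds 497.5/213.5 = 2.33; placebo odds 5.95/104.05 = 0.057; odds ratio 40.7.
- Ratio 11.6/40.7 = 0.28.

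With the variance as the sum of 1/(n p q) at the penalised estimates, and all k placebo positives nonresponders:

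| k | OR, positive | OR, negative | Ratio (95% CI) | Chance all k are nonresponders |
|---|---|---|---|---|
| 1 | 7.0 | 40.8 | 0.17 (0.002 to 17.2) | 0.95 |
| 2 | 11.6 | 40.7 | 0.28 (0.006 to 13.1) | 0.90 |
| 4 | 20.9 | 40.7 | 0.51 (0.017 to 15.2) | 0.81 |
| 6 | 30.2 | 40.6 | 0.74 (0.029 to 19.0) | 0.74 |

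Every interval spans more than 500-fold. If the variance is instead the sum of 1/(x + 0.5) + 1/(n − x + 0.5), the narrowest case (k = 6) has variance 2.154 + 0.184 + 0.027 + 0.007 = 2.37 and still spans exp(2 × 1.96 × √2.37), or about 418-fold.

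**Simulation** (200,000 draws, placebo response 5%, first variance). For k = 2, 4 and 6 the median ratio is 0.26, 0.43 and 0.57 when the truth is 1. The flag rate at 0.10 is 8.7%, 11.7% and 10.2%, close to nominal.

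**Detection.** Suppose mirikizumab positives truly respond at 50% and negatives at 75%. With 2 to 6 placebo positives the interaction test flags this about 14% to 66% of the time, depending on the variance form and on whether placebo response is 5% (sPGA) or 3% (PASI 90). The SAP fixes no test statistic or standard error. The same 25-point contrast within mirikizumab has a 95% half-width of 1.96 × √(0.25/178 + 0.1875/710) = 8.0 points.

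**Negative category.** If positives respond at 50% and the whole mirikizumab arm at 70%, the displayed difference is (0.70 − 0.50t)/(1 − t) − 0.05. That is 67.2, 70.0 and 73.6 points for a TE-ADA rate t of 10%, 20% and 30%, against 65.0 in the ITT population.

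**Steroid subgroups.** Let use depend on response alone, with rate a in responders and b in nonresponders (both assumed). Response p in users becomes pa/[pa + (1 − p)b].

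- a = 5%, b = 30%: users 0.280 vs 0.009 (27 points); non-users 0.760 vs 0.067 (69 points).
- a = 10%, b = 20%: 51 and 67 points.
- The odds ratio is 44.3 in every stratum, equal to the whole-arm value (0.70/0.30)/(0.05/0.95).
- If 40% of placebo nonresponders use steroids while the other rates stay at 5% and 30%, the odds ratios are 59 and 38, and the flag rate is about 12%.
- At Week 52 against secukinumab (75% vs 65%), 5%/30% gives 9.7 and 8.7 points against 10.0, so there is little distortion.

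**The case against.** The size of the Week 16 problem rests on rates the documents do not give. If TE-ADA is uncommon, the 10% rule stops testing. If no placebo patient is positive, no interaction estimate appears to mislead anyone. Much of the remedy is also planned already: Section 6.15.1 displays response by treatment within each category, Section 6.1.2 gives group proportions with confidence intervals, and Section 6.14.6 defers further immunogenicity and efficacy work to the integrated analysis. All of this stands. It makes the change mainly a removal of between-arm output, and it keeps the priority low. It does not give the positive category a comparator.

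A reader might infer more on four counts, which the documents do not support:

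- **A contradiction at Week 52.** Section 6.15.1 names no arms. Section 6.14.6 places the TE-ADA efficacy subgroup within immunogenicity, and the Table AMAJ.6.2 note removes secukinumab comparisons for immunogenicity analysis. Read together, the specific note governs. Only a cross-reference is missing.
- **A breach of the SAP's own rule.** Section 6.3.5 calls conditioning on a postrandomisation event non-causal and limits that analysis to description, but it speaks of the as-observed analysis only. Table AMAJ.6.6 plans CMH comparisons among Week 16 and Week 24 responders, so there is no SAP-wide descriptive-only rule.
- **An inflated false-positive rate, or one definite figure for low power.** With 2 to 6 placebo positives the flag rate is near nominal, and detection varies widely with choices that the SAP leaves open.
- **Invalid steroid tests.** The odds-ratio interaction test and forest plots barely move. Systemic use is barred for 28 days before baseline (exclusion criterion 24) and on study is limited to short-term management of adverse events (Table AMAJ(1).2), so the 10% rule may remove testing there. At assumed use of 2% and 10%, users are 5.0% of patients.

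**Conclusion.** The point holds for TE-ADA at Week 16. Treatment comparisons and an interaction test are planned for a status that placebo patients can hardly acquire, and the size rule does not prevent them. Under the stated assumptions (20% TE-ADA on mirikizumab, 2 to 6 placebo positives, 70% vs 5% response) the interaction ratio is centred on 0.26 to 0.57 when it should be 1, and is too imprecise to interpret. With no placebo positives it does not exist. Below about 11.3% or 16.3% TE-ADA the size rule would cancel testing.

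The steroid subgroups are a secondary matter. Only the displayed Week 16 risk differences could mislead, and only if use follows nonresponse. These analyses are exploratory and lie outside the multiplicity graph.

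**What to change.** In Section 6.15.1, take TE-ADA status out of the common plan. Report response by TE-ADA status descriptively within the mirikizumab arms at Weeks 16 and 52: counts, proportions and 95% confidence intervals, with no between-arm differences, odds ratios, p-values or interaction test. Add a cross-reference to the Table AMAJ.6.2 note on secukinumab.

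Optionally, label the two concomitant-steroid subgroups as partly or wholly post-randomisation, and their within-category differences as not causal.

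The cost is SAP wording and the loss of a few exploratory p-values and forest-plot rows. The Table AMAJ.4.1 endpoint on TE-ADA and efficacy names no comparator, so it is still fully reported.

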6.15.2. Safety Subgroup Analyses

Subgroup analysis for safety related endpoints will be performed within the context of the integrated safety analysis. No safety subgroup analysis will be performed specifically for this study unless there is a potentially relevant finding during the periodic study safety reviews.

6.16. Analysis for Japan Submission

A subset of the planned efficacy, health outcomes and safety analyses will be reproduced based on patients from Japan sites, in support of the regulatory submission in Japan. The list of tables, listings, and figures for the patients from Japan sites (Japanese population) will be in a separate document.

Protocol Addendum I6T-MC-AMAJ (1.1) is performed in Japan to enable the inclusion of patients with generalized pustular psoriasis (GPP) and erythrodermic psoriasis (EP) to fulfill the needs for Japan submission. [Appendix 2](#) provides the details of the Analysis Plan for the Japan Addendum.

6.17. Analysis for Australian Submission

In addition to the analysis already specified, a subset of planned efficacy analyses will be conducted to meet the Pharmaceutical Benefits Advisory Commission (PBAC) criteria. The PBAC population is a subset of the patients with a PASI score >15 at baseline in the ITT Population. The sPGA (0,1), sPGA (0), PASI 75, PASI 90 and PASI 100 using the PBAC population will be analyzed for Induction Period, and combined Induction and Maintenance Periods.

6.18. Protocol Deviations

Protocol deviations will be identified throughout the study. Important protocol deviations are defined as those deviations from the protocol likely to have a significant impact on the completeness, accuracy, and/or reliability of the study data or that may significantly affect a patient's rights, safety, or well-being.

The major protocol deviations, which are the subset of the important protocol deviations, are the protocol deviations that might have impact on the efficacy and/or safety results. The impact of

major protocol deviations on the efficacy results will be investigated by assessing the robustness of the study results and conclusions to the choice of analysis population, both by including and excluding the data potentially affected by major protocol deviations.

A separate document known as the “The AMAJ Trial Issues Management Plan” describes the categories and subcategories of important protocol deviations, whether or not these deviations are major protocol violations, the action to be taken regarding the exclusion of patients from PPS and the source of the deviation identified.

The number and percentage of patients having important protocol deviation(s) will be summarized within category and subcategory of deviations by treatment for the ITT population in the Induction Period and the combined Induction and Maintenance Periods.

A by-patient listing of important protocol deviations will be provided.

6.19. Interim Analyses and Data Monitoring

Data Monitoring Committee: One DMC consisting of members external to Lilly will be established for interim safety monitoring across Studies I6T-MC-AMAK, AMAJ, and AMAH in patients with psoriasis. This committee will consist of a minimum of 3 members, including a physician with expertise in dermatology and a statistician. No member of the DMC may have contact with study sites. A Statistical Analysis Center (SAC) will prepare and provide unblinded safety data to the DMC. The SAC members may be Lilly employees or from third-party organizations designated by Lilly. However, they will be external to the study team and will have no contact with sites and no privileges to influence change in the ongoing study. Access to the unblinded safety data will be limited to the DMC and the SAC or their designees. The study team will not have access to the unblinded data. Only the DMC is authorized to evaluate unblinded data. The purpose of the DMC is to advise Lilly regarding continuing patient safety; however, the DMC may request key efficacy data to put safety observations into context and to confirm a reasonable benefit/risk profile for ongoing patients in the study. Hence, there will be no alpha adjustment for these interim assessments. Study sites will receive information about interim assessments ONLY if they need to know for the safety of their patients. This committee will make recommendations as to whether it is scientifically and ethically appropriate to continue enrollment, discontinue a treatment group, or discontinue the study. Details outlining the roles and responsibilities of the DMC will be finalized in the DMC charter and an associated DMC analysis plan prior to the first unblinded assessment.

Week 52 Database lock (DBL): An unblinded analysis will be performed after all patients have completed the Week 52 Visit or discontinued study treatment. This DBL will include all data collected by the cut-off date including follow-up data from patients that have begun the Posttreatment Follow-Up Period. This is the final analysis for the efficacy endpoints up to Week 52. However, the study may be ongoing for the Posttreatment Follow-Up Period at the time of this DBL.

Final DBL: A final DBL will occur after the Posttreatment Follow-Up Period is completed.

Pharmacokinetics Analysis: In addition, a limited number of preidentified internal Lilly personnel that are not in contact with clinical sites may gain access to unblinded data including PK, as specified in the unblinding plan, after all patients have completed Week 40 visit or discontinued study treatment, in order to initiate the population PK model development processes. The unblinded data will be restricted and will NOT be shared with anyone outside this preidentified group until after the Week 52 DBL. Unblinding details will be provided in the unblinding plan.

6.20. Annual Report Analyses

Based on regulatory requirements for the Development Safety Update Report (DSUR), reports will be produced (if not already available from the study CSR) for the reporting period covered by the DSUR.

6.21. Clinical Trial Registry Analyses

Additional analyses will be performed for the purpose of fulfilling the Clinical Trial Registry (CTR) requirements.

Analyses provided for the CTR requirements include the following:

Summary of AEs, provided as a dataset which will be converted to an XML file. Both Serious Adverse Events (SAEs) and 'Other' AEs are summarized: by treatment group, by MedDRA PT.

- An AE is considered 'Serious' whether or not it is a TEAE.
- An AE is considered in the 'Other' category if it is both a TEAE and is not serious. For each SAE and 'Other' AE, for each term and treatment group, the following are provided:
 - the number of participants at risk of an event
 - the number of participants who experienced each event term
 - the number of events experienced.
- Consistent with www.ClinicalTrials.gov requirements, 'Other' AEs that occur in fewer than 5% of patients/subjects in every treatment group may not be included if a 5% threshold is chosen (5% is the minimum threshold).
- AE reporting is consistent with other document disclosures for example, the CSR, manuscripts, and so forth.

7. Unblinding Plan

Unblinding details are specified in a separated unblinding plan.

8. References

- Agresti A. Categorical Data Analysis. 3rd Edition. Hoboken, NJ: John Wiley & Sons; 2013.
